9.10 Removal of Subjects

Subjects may withdraw from the study at any time at their own request. Subjects may be withdrawn from study drug treatment at any time at the discretion of the investigator or Vertex for safety reasons, behavior, noncompliance with study drug dosing or study procedures, ineligibility, or administrative reasons.

Whenever possible, subjects who have been withdrawn from study drug treatment will continue on study, however, Vertex retains the right to remove a subject from the study.

Subjects who have been randomized and whose screening *CFTR* genotype does not confirm study eligibility must be discontinued from the study, even if a previous *CFTR* genotype laboratory report was used to establish eligibility.

If a subject does not return for a scheduled visit, reasonable effort will be made to contact the subject. In any circumstance, reasonable effort will be made to document subject outcome. The investigator will inquire about the reason for withdrawal, request that the subject return all unused investigational product(s), request that the subject return for a Safety Follow-up Visit, if applicable (see Section 9.1.6), and follow up with the subject regarding any unresolved AEs.

If the subject withdraws consent for the study, no further evaluations will be performed and no additional data will be collected. Vertex may retain and continue to use the study data and samples collected. The study data and the samples may be used for the development of the study compound, other drugs, or diagnostics, in publications and presentations, or for education purposes. If the subject withdraws from the study, the study data and samples collected will remain part of the study. A subject will not be able to request the withdrawal of his/her information from the study data. A subject may request destruction of the samples collected from him/her during the study as long as those samples can be identified as his/her samples. Any information that already has been obtained from the samples will continue to be used.

9.11 Replacement of Subjects

Subjects who withdraw or are withdrawn before the first dose of study drug may be replaced.

Subjects who withdraw or are withdrawn for non-safety reasons during the study drug treatment period may be replaced at Vertex's discretion.

10 STUDY DRUG ADMINISTRATION AND MANAGEMENT

Study drug refers to VX-659, TEZ, TEZ/IVA, IVA, VX-561, and their matching placebos.

10.1 Preparation and Dispensing

Study drug may be dispensed only under the supervision of the investigator or an authorized designee and only for administration to the study subjects.

10.2 Packaging and Labeling

Study drug tablets will be supplied in blister cards by Vertex. Study drug labeling will be in compliance with applicable local and national regulations. Additional details regarding packaging, labeling, and dispensing for study drug will be included in the Pharmacy Manual.

10.3 Study Drug Supply, Storage, and Handling

VX-659 and matching placebo will be supplied as tablets of similar size and appearance containing 80 mg VX-659 and 0 mg VX-659, respectively (Table 10-1).

TEZ/IVA (100 mg/150 mg) and matching placebo will be supplied as film-coated tablets of similar size and appearance containing 100 mg TEZ/150 mg IVA and 0 mg TEZ/0 mg IVA, respectively (Table 10-1).

IVA (150 mg) and matching placebo will be supplied as film-coated tablets of similar size and appearance containing 150 mg IVA and 0 mg IVA, respectively (Table 10-1).

TEZ and matching placebo will be supplied as tablets of similar size and appearance containing 50 mg TEZ and 0 mg TEZ, respectively (Table 10-1).

VX-561 and matching placebo will be supplied as tablets of similar size and appearance containing 50 mg VX-561 and 0 mg VX-561, respectively (Table 10-1).

Blister cards must be stored under conditions noted in the Pharmacy Manual. The investigator, or an authorized designee (e.g., a licensed pharmacist), will ensure that all investigational product is stored in a secured area, under recommended storage conditions, and in accordance with applicable regulatory requirements. To ensure adequate records, all study drugs will be accounted for via the drug accountability forms as instructed by Vertex.

Table 10-1 Study Drug: Strength/Formulation/Route

Drug Name	Strength/Formulation/ Route
VX-659	80-mg tablet, oral
VX-659-matching placebo	0-mg tablet, oral
TEZ/IVA fixed-dose	100-mg/150-mg tablet; oral
TEZ/IVA-matching placebo	0-mg/0-mg tablet; oral
IVA	150-mg tablet, oral
IVA-matching placebo	0-mg tablet, oral

Table 10-1 Study Drug: Strength/Formulation/Route

Drug Name	Strength/Formulation/ Route
TEZ	50-mg tablet, oral
TEZ-matching placebo	0-mg tablet, oral
VX-561	50-mg tablet, oral
VX-561-matching placebo	0-mg tablet, oral

IVA: ivacaftor; TEZ: tezacaftor

10.4 Drug Accountability

The pharmacist or designated study site staff will maintain information regarding the dates and amounts of study drug received; study drug dispensed to the subjects; and study drug returned by the subjects. Subjects will be instructed to return all used and unused materials associated with the study drug to the site. These materials will be retained at the site according to instructions provided by Vertex or its designee until inventoried by the study monitor. The study monitor will review study drug records and inventory throughout the study.

10.5 Disposal, Return, or Retention of Unused Drug

The study site staff or pharmacy personnel will retain all materials returned by the subjects until the study monitor has performed drug accountability. At the end of the study, the study monitor will provide instructions as to the disposition of any unused investigational product. If the study monitor authorizes destruction at the study site, the investigator will ensure that the materials are destroyed in compliance with applicable environmental regulations, institutional policy, and any special instructions provided by Vertex. Destruction will be adequately documented.

10.6 Compliance

To ensure treatment compliance, the investigator or designee will supervise all study drug dosing that occurs at the site. At each visit, site personnel will review that the subject is compliant with study drug dosing and remind the subject of study drug dosing requirements. Compliance will also be assessed by ongoing study drug count.

If a subject demonstrates continued noncompliance of study drug dosing despite educational efforts, the investigator will contact the medical monitor to discuss discontinuing the subject from the study.

10.7 Blinding and Unblinding

This will be a double-blind study.

10.7.1 Blinding

All subjects, site personnel (including the investigator, the site monitor, and the study team), and the Vertex study team will be blinded to the treatment codes with the exception of the following:

- Any site personnel for whom this information is important to ensure the safety of the subject in the event of a life-threatening medical emergency
- Any site personnel for whom this information is important to ensure the safety of the subject and her fetus in the event of a pregnancy
- Vertex Global Patient Safety (GPS) and Regulatory Affairs personnel to satisfy serious adverse event (SAE) processing and reporting regulations
- Unblinded statistician preparing the final (production) randomization list who is not part of the study team
- Vertex IWRS Manager
- Vertex Clinical Supply Chain
- IDMC
- Vendor performing the interim analyses (IAs) and preparing the unblinded analysis for the ongoing reviews of efficacy and safety data, and the IDMC
- Bioanalytical contract research organization (CRO) analyzing PK samples and Vertex Bioanalytical personnel who are not members of the study team may review raw data from Bioanalytical CRO.
- Vertex Modeling and Simulation personnel or vendor conducting the population PK and PK/PD analyses
- Vertex medical monitor may, for matters relating to safety concerns, unblind individual subjects at any time

Blinding of Sweat Chloride and Spirometry Results:

- The Vertex study team will not have access to sweat chloride or spirometry results after a subject receives the first dose of study drug on the Day 1 Visit until after the data are unblinded for full review per Section 12.3.6.1.
- Sites, subjects, and their parents/caregivers/companions should not be informed of a subject's study-related sweat chloride results until after the subject's last study visit, even if the subject prematurely discontinues treatment.
- Subjects and their parents/caregivers/companions should not be informed of the subject's study-related spirometry results until after the subject's last study visit, even if the subject prematurely discontinues treatment.

10.7.2 Unblinding

At the initiation of the study, the study site will be instructed on the method for breaking the blind. The unblinding method will be either a manual or electronic process.

Unblinding of Individual Subject Treatment Assignments by Investigator for Medical Emergencies or Urgent Clinical Situations

Unblinding of the individual subject's treatment by the investigator will be limited to medical emergencies or urgent clinical situations in which knowledge of the subject's study treatment is necessary for clinical management. In such cases, investigators will use their best judgment as to

whether to unblind without first attempting to contact the medical monitor to discuss and agree to the need for unblinding. If investigators deem it not necessary to unblind immediately, they will first attempt to contact the medical monitor to discuss and agree to the need for unblinding. If investigators have tried but are unable to reach the medical monitor, they will use their best judgment, based on the nature and urgency of the clinical situation, and may proceed with unblinding without having successfully reached and discussed the situation with the medical monitor.

Contact information for the medical monitor (or appropriate backup) will be provided in a separate document.

In addition, the Vertex Medical Information Call Center [REDACTED] will answer calls 24 hours a day, 7 days a week, 365 days of the year, and will triage these calls to the study medical monitor or appropriate backup.

If a subject's treatment assignment has been unblinded for a medical emergency or urgent clinical situation, the medical monitor will be notified within 24 hours of the unblinding event. The reason and the date of the unblinding will be documented clearly in the subject's study file. Information about the treatment assignment obtained from the unblinding will be maintained in a secure location with controlled access and will not be shared with the sponsor (Vertex), CRO, or any site personnel (other than the physician treating the subject). In addition, the investigator will consider whether the clinical event that prompted unblinding will be considered an SAE, according to the regulatory definitions or criteria for SAEs, and if so, submit an SAE report to Vertex GPS or designee, per Section 13.1.2.

Unblinding of Individual Subject Treatment Assignments by Vertex GPS or Designee for SAEs or Safety Concerns

Vertex GPS or designee will unblind any SAE reports in compliance with regulatory reporting requirements. In addition, Vertex may, for matters relating to safety concerns, unblind individual subjects at any time.

Unblinded Reviews of Data by Vertex for Administrative Purposes (Planning, Decision-making, and Regulatory Submission)

A limited Vertex team will be unblinded and have access to safety, efficacy, and PD data for the purpose of conducting ongoing reviews of safety and efficacy data for planning and enabling clinical development. Members of the limited unblinded Vertex team will not be part of the Vertex study team and will not be involved in or influence the conduct of the study.

Unblinding: Interim Analysis Results

Interim analyses may be conducted for any part of the study after at least 50% of subjects in the part have completed the Day 15 Visit (see Section 12.3.6.1). Each IA will only include data for a single part of the study. The results of these analyses will be reviewed by a limited Vertex team. When an IA is performed after all subjects in a part have completed the Safety Follow-up Visit, results from that part will be unblinded for full review by the Vertex study team.

11 ASSESSMENTS

The Schedules of Assessments are shown in [Table 3-1](#) (Part 1), [Table 3-2](#) (Part 2), and [Table 3-3](#) (Part 3).

11.1 Timing of Assessments

The CFQ-R assessment must be completed before any other assessment at the clinic visits when it is required. Other assessments may be performed in any order when more than 1 assessment is required at a particular time point.

11.2 Subject and Disease Characteristics

Subject and disease characteristics include demographics, medical history, height, and weight.

Medical history will be elicited from each subject and extracted from medical records during screening. Based on the medical history, the subject will be assessed for any disqualifying medical conditions as specified in the inclusion and exclusion criteria. The medical history will include a complete review of systems, past medical and surgical histories, and any allergies.

Height and weight will be measured with shoes off.

11.3 Pharmacokinetics

11.3.1 Blood Sampling

Blood samples will be collected to determine plasma concentrations of VX-659, TEZ, M1-TEZ, IVA, M1-IVA, and VX-561. These samples may also be used for evaluation of VX-659 or VX-561 metabolites, for evaluation of additional TEZ or IVA metabolites, for further evaluation of the bioanalytical method, and for exploratory analyses that provide information on the metabolic pathways used by or affected by VX-659; these results may not be included in the clinical study report.

All efforts will be made to obtain the PK samples at the exact nominal time relative to dosing. Acceptable windows for sampling times are shown in [Table 11-1](#). Samples collected outside of these acceptable windows will be considered protocol deviations.

Table 11-1 Acceptable Pharmacokinetic Sampling Windows

Sampling Time	Time From Scheduled Sampling Allowed
Predose	- 60 minutes
From 0.25 up to ≤ 8 hours after study drug dosing	± 15 minutes

For each visit with a PK blood draw, a record of study drug administration will be collected as described in [Section 9.7](#). The collection date and exact time that each PK blood sample is drawn will also be recorded.

Samples from the PK sampling will be kept frozen by Vertex or its designee until all analyses have been completed and then disposed of according to Vertex or designee standard operating procedures.

Plasma concentration samples collected from subjects treated with placebo will not be routinely analyzed.

11.3.2 Processing and Handling of Pharmacokinetic Samples

Detailed procedures for the collection of blood samples and further procedures for processing and handling of samples for PK analysis will be provided in the PK Sample Handling Guidelines.

11.3.3 Bioanalysis

Samples will be analyzed using 1 or more validated analytical methods in compliance with Vertex or designee standard operating procedures. A description of the assay and validation data will be provided in separate reports.

11.4 Pharmacodynamics

Collection of sweat samples will be done with an approved collection device. At each time point, 2 samples will be collected, 1 from each arm (left and right). Sweat samples will be sent to a central laboratory for testing and interpretation of results. Individual sweat chloride test results will not be disclosed to the study sites after those from pre-dose on the Day 1 Visit. Specific instructions for collection, handling, processing, and shipping of sweat chloride samples to the central laboratory will be provided separately. See Section 10.7.1 for information about blinding of sweat chloride results.

11.6 Efficacy

11.6.1 Spirometry

Spirometry will be performed according to the American Thoracic Society Guidelines/European Respiratory Society Guidelines¹³ and the following additional guidelines:

Pre-bronchodilator spirometry is defined as spirometry testing performed for subjects who have

- withheld their short-acting bronchodilators (e.g., albuterol) or anticholinergic (e.g., ipratropium bromide [Atrovent[®]]) for more than 4 hours before the spirometry assessment;
- withheld their long-acting bronchodilator (e.g., salmeterol) for more than 12 hours before the spirometry assessment; and
- withheld their once-daily, long-acting bronchodilator (e.g., tiotropium bromide [Spiriva[®]]) for more than 24 hours before the spirometry assessment.

During the Screening Period, spirometry assessments may be performed pre- or post-bronchodilators. At all other visits, all spirometry assessments should be performed

“pre-bronchodilator.” During the Treatment Period, spirometry assessments must be performed before the in-clinic dose of study drug, at approximately the same time at each visit.

If a subject forgets to withhold bronchodilator(s), spirometry should be performed according to the following:

- If a subject’s Day 1 Visit spirometry assessment is pre-bronchodilator, but, on a subsequent visit, the subject forgets to withhold bronchodilator use, a post-bronchodilator spirometry assessment will be obtained for that visit only, and the visit will not be rescheduled.
- If, on the Day 1 Visit, the subject forgets to withhold his/her dose of bronchodilator, spirometry should be performed post-bronchodilator, and all subsequent spirometric measurements should be performed post-bronchodilator.
- Each spirometry assessment will be recorded in the source documents as pre- or post-bronchodilator.

If more than 1 spirometry assessment is required at a visit, bronchodilators will be withheld until completion of the last scheduled spirometry assessment.

All sites will be provided with spirometers to be used for all study assessments. Spirometry data will be transmitted to a centralized spirometry service for quality review.

See Section 10.7.1 for information about blinding of spirometry results.

The measured spirometric values listed below will be converted to percent predicted values using the GLI standards.¹²

- FEV₁ (L)
- Forced vital capacity (FVC) (L)
- FEV₁/FVC (ratio)
- Forced expiratory flow (FEF_{25%-75%}) (L/s)

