^j Complete and abbreviated physical examinations (PEs) are described in Section 11.7.3. Symptom-directed PEs can be done at any time at the discretion of the investigator or healthcare provider.

^k Vital signs and pulse oximetry will be collected after the subject has been seated for at least 5 minutes.

^l Standard 12-lead ECGs will be performed after the subject has been rested for at least 5 minutes. On the Day 1 and 15 Visits, ECGs will be collected before dosing and 5 hours (± 1 hour) after dosing. At other visits, ECGs will be collected before dosing (as applicable). ECGs collected on the Day 1 Visit before dosing will be performed in triplicate.

^m See inclusion criterion 5 for information about the sweat chloride assessment for study eligibility. Sweat chloride assessments should be done at approximately the same time at every study visit during the Treatment Period and follow-up.

ⁿ At the Screening Visit, spirometry may be done pre- or post-bronchodilator. At other study visits, spirometry will be done pre-bronchodilator, before the in-clinic dose of study drugs, and should be performed at approximately the same time at every visit. On the Day 1 and 15 Visits, spirometry will also be performed 5 hours (± 1 hour) after the in-clinic dose of study drugs.

^o CFQ-R must be completed before the start of any other assessments scheduled at that visit.

^p The predose assessment on the Day 1 Visit may be performed on the previous day (Day -1) if randomization has occurred.

^q FSH will be measured for any potential postmenopausal female subjects with at least 12 months of continuous spontaneous amenorrhea.

Table 3-1 Study VX16-659-101 Part 1 (Subjects with F/MF genotypes): Schedule of Assessments

Event/Assessment ^a	Screening Period		Treatment Period (5 weeks)				ETT Visit ^b	Safety Follow-up 28 (± 7) Days After Last Dose
			Period 1 ^c (4 weeks)			Period 2		
	Screening Visit Days -28 to -1	Stratification Visit ^d Day -27 to -1	Day 1	Day 15 (± 2 days)	Day 29 (± 2 days)	Day 33 Visit ^e		
G6PD activity test ^f	X							
Serum chemistry and hematology ^g	X		X	X	X	X	X	
Coagulation ^g	X		X	X	X		X	
PK sampling ^h			X	X	X	X	X	
AEs, medications ⁱ , treatments, and procedures	Continuous from signing of the ICF through the Safety Follow-up Visit							

^f Blood samples will be collected for the G6PD activity test.

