8.4.7 Other Safety Analysis

8.4.7.1 Post-dose Spirometry

A summary of the pre-dose values for ppFEV₁ and change from pre-dose value for the post-dose ppFEV₁ value at 5 hours post-dose will be presented on nominal visits Day 1 and Day 15, by treatment group, for each part. Further, a box plot of differences (post-dose - pre-dose) will be presented by visit and treatment group, for each part.

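### Protocol 11.6.1 conflicts on bronchodilator use before the 5-hour spirometry test, so some post-dose minus pre-dose differences in SAP 8.4.7.1 may contain short-acting bronchodilator wear-off

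*Protocol*

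**What the plan says.** The schedules of assessments for all three parts (Table 3-1 footnote n; Tables 3-2 and 3-3 footnote m) add a second test at two visits: "On the Day 1 and 15 Visits, spirometry will also be performed 5 hours (± 1 hour) after the in-clinic dose of study drugs".

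Protocol 11.6.1 then gives three instructions that bear on that second test:

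- A subject who did not withhold on Day 1: "spirometry should be performed post-bronchodilator, and all subsequent spirometric measurements should be performed post-bronchodilator". Nothing limits this to later visits.
- A subject who did withhold on Day 1 but forgets at a later visit: "a post-bronchodilator spirometry assessment will be obtained for that visit only, and the visit will not be rescheduled". This speaks of one assessment and does not mention a second test at the same visit.
- Any visit with more than one test: "If more than 1 spirometry assessment is required at a visit, bronchodilators will be withheld until completion of the last scheduled spirometry assessment". No exception is made for a subject who has already taken a bronchodilator.

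The same section defines a test as pre-bronchodilator when a short-acting bronchodilator or anticholinergic has been withheld "for more than 4 hours before the spirometry assessment". The limits are 12 hours for long-acting and 24 hours for once-daily long-acting drugs. Each test's status is to be noted in the source documents.

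SAP 8.4.7.1 summarises the change from the pre-dose to the 5-hour value on Days 1 and 15, and adds that "a box plot of differences (post-dose - pre-dose) will be presented by visit and treatment group, for each part". It does not refer to bronchodilator status.

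**The concern.** For a subject who did not withhold on Day 1, two sentences of one section point in opposite directions about the 5-hour test. Sites could follow either, so handling may differ between sites. Under one of the two, the paired difference compares tests done in different bronchodilator states, and the SAP has no rule for recognising such a pair.

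Spirometry is a safety endpoint in SAP 5.2 and 8.4, and this display is the only acute post-dose lung-function analysis in the supplied SAP text. In a subject with a mixed pair, loss of bronchodilator effect lowers the second value. It can be mistaken for an acute fall after dosing, or can mask an acute rise. With few subjects per arm, one such value is visible in the box plot.

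**Working it through.** The plan states no figure on this point, so there is none to reproduce. The check has three steps.

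**1. Does the status change between the two tests?** Inputs: the second test is 4 to 6 hours after the study dose (schedule footnotes); the study dose follows the pre-dose tests; the status limits are 4, 12 and 24 hours (Protocol 11.6.1). Time from bronchodilator to second test = (time from bronchodilator to study dose) + (4, 5 or 6 h).

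| Drug type | Limit | Second test counts as pre-bronchodilator if the drug was taken before the study dose by more than (test at 4 / 5 / 6 h) |
|---|---|---|
| Short-acting or anticholinergic | 4 h | 0 / 0 / 0 h: always |
| Long-acting | 12 h | 8 / 7 / 6 h |
| Once-daily long-acting | 24 h | 20 / 19 / 18 h |

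A short-acting drug taken before the pre-dose test, with no further dose, is therefore always more than 4 hours old at the second test. A long-acting drug taken shortly before the visit leaves both tests post-bronchodilator.

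**2. Which pairs are mixed?**

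- *Did not withhold on Day 1, "all subsequent spirometric measurements should be performed post-bronchodilator" followed:* both tests are post-bronchodilator. For a short-acting drug this needs a further dose, which the withholding sentence rules out.
- *Did not withhold on Day 1, "bronchodilators will be withheld until completion of the last scheduled spirometry assessment" followed:* after a short-acting drug the Day 1 pair is mixed. The same happens on Day 15 if the first test is done post-bronchodilator, as the Day 1 rule directs, and the drug is then withheld.
- *Forgot only on Day 15:* the specific rule is silent on the second test. Following the withholding sentence again gives a mixed pair after a short-acting drug.

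**3. How large could it be?** The documents give neither the wear-off d nor how often it occurs. Assume d = 3 to 8 ppFEV1 points in one subject. Shift in the arm mean difference = -d/n. Arm sizes follow from the ratios in Protocol Table 9-1: Part 1, 54 subjects at 1:1:2:2, gives 9, 9, 18, 18; Part 2, 27 at 1:2, gives 9, 18; Part 3, 24 at 1:3, gives 6, 18.

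| n | d = 3 | d = 8 |
|---|---|---|
| 18 | -3/18 = -0.17 | -8/18 = -0.44 |
| 9 | -3/9 = -0.33 | -8/9 = -0.89 |
| 6 | -3/6 = -0.50 | -8/6 = -1.33 |

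If a share q of subjects has a mixed pair in every arm, the expected shift is -q x d in every arm, control included. Chance imbalance remains. The probability that an 18-subject arm has at least one mixed pair and a control arm of size c has none is [1 - (1 - q)^18] x (1 - q)^c. With q as an assumption:

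| q | c = 9 | c = 6 |
|---|---|---|
| 2% | 25% | 27% |
| 5% | 38% | 44% |
| 10% | 33% | 45% |
| 20% | 13% | 26% |

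Here q is the share with a mixed pair. It cannot exceed the share who did not withhold, and is lower when long-acting drugs are involved or the other sentence is followed.

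**The case against.** The strongest reply is that 11.6.1 can be read as a general withholding rule with specific exceptions for subjects who forget, the exception prevailing. On that reading both Day 1 tests are post-bronchodilator and no status change arises. This is a fair reading, but the text does not state it, and the withholding sentence comes last and without exceptions. The need for clarification stands; proof of bias does not follow.

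A reader might infer an apparent acute fall specific to active treatment. The documents do not support that. Placebo and TEZ/IVA subjects have the same paired tests under the same instructions, and allocation is randomised and blinded, so the expected shift is equal across arms.

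A reader might also extend the point to the post-dose sensitivity analysis mentioned in SAP 8.3.1.1.1. Its description is not in the supplied text. The Appendix B note allowing a post-dose value for imputation at Day 15 concerns substituting a value, not forming a within-visit pair. No claim is made about it here.

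The consequences are also limited. The protocol calls the safety analysis descriptive, its own safety endpoints (7.1, 12.3.5) omit spirometry, and no stopping rule uses this difference. Individual data will be listed. All of this stands and keeps the point modest.

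Finally, removing mixed pairs could discard a genuine acute fall. That objection is accepted and shapes the fix.

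**Conclusion.** The two sentences conflict on their literal wording for the 5-hour test in a subject who did not withhold on Day 1, and the text is silent on the second test for one who forgets only at Day 15. The consequence is conditional: the difference in SAP 8.4.7.1 may contain wear-off when the withholding sentence is followed, and the change of status is certain only for drugs with the 4-hour limit.

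Where it occurs, it can look like an acute fall in an individual or a within-group summary. It is not a systematic between-arm bias, although arms of 6 to 18 may be unbalanced by chance. The sizes above rest on an assumed 3 to 8 points that has fully worn off by the second test.

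The planned primary model uses pre-dose values (SAP 8.3.1.1.1) and is not affected by this route. This is a correctable weakness in one descriptive safety display.

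**What to change.** - **Protocol 11.6.1:** reconcile the two sentences so that one instruction governs the second same-visit test for a subject who did not withhold, on Day 1 or only at Day 15. Which instruction is right is for the sponsor to decide.
- **Data:** carry the pre- or post-bronchodilator status of each test into the analysis data. The protocol places it in source documents; nothing in the supplied text shows that it reaches the database.
- **SAP 8.4.7.1:** keep all pairs, flag and list those whose two tests differ in status, and show the summary and box plot with and without them.

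The flag has a limit: two post-bronchodilator tests hours apart can still differ in time since the bronchodilator. The cost is a clarified instruction, a small amount of extra data capture and one extra descriptive display.
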